3.5 Sample Size In total, 100 patients will be enrolled in a 1:1 ratio between the two treatment groups. This will ensure that the minimum of 90 patients required to answer the study question are followed up for the duration of the study. The enrolment goal is to have at least 45 patients in each of the two treatment groups completing the study. Sample size calculation and statistical analysis are more comprehensively detailed in section 6.

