6.0 Statistical Methods

6.1 Power / Sample size calculation

Primary Outcome measure: Functional outcome as assessed using the FJS score at two years following Mako-arm assisted TKA.

Using data from our initial cohort recording functional outcomes, the mean FJS score at 1 year in the mFA TKA was 59 (SD 6) and in the kFA TKA was 75 (SD 8). It is assumed that MA results will be no better than mFA results. The study was powered to demonstrate a 12 point difference in the Forgotten Joint score, which is the minimal clinical important change in the score. Using a one tailed analysis (assuming superior results with the kFA), an alpha value of 0.05 and power of 0.80, and accounting for expected drop-out rate of 10%, this study will need 100 patients to answer the study question.

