6.2 Endpoint Analysis

6.2.1 Primary Endpoint

The analysis of the per-protocol population will be considered the primary analysis. The differences

between the MA TKA and FA TKA groups will be analysed by calculating the difference from baseline, per patient, and a two-sided confidence interval for the difference between the changes from baseline will be calculated. This confidence interval will cover the true difference in the percentage change from baseline with a probability of 95%.

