6.2.2 Secondary Endpoints

Standard statistical methods will be employed to analyse the data. It is anticipated that the following techniques may be used: descriptive statistics, t-test, paired t-test, analysis of variance, Fisher exact test, Chi-square test, and graphical displays. Assumptions of normality will be tested with the Shapiro-Wilk test. Assumptions of homogeneity of variance will be tested with Levene's test. If the distributional assumptions are (severely) violated, non-parametric techniques, such as Mann-Whitney's test will be employed.

All tests will be declared statistically significant if the calculated p-value is less or equal to 0.05. All tests will appear as two-sided p-values. Summary statistics will consist of numbers and percentages of responses in each category for discrete measure, and of means, medians, standard deviation, 95% confidence interval, minimum, maximum for continuous measures, and will be presented per treatment group.

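### Section 6.1 sizes the trial with a one-tailed 0.05 test, but the primary analysis is a two-sided 95% interval, so the stated 80% power does not belong to the planned analysis

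*Combined protocol and SAP*

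**What the plan says.** **Sizing (6.1, with 3.5).** The calculation is described as "Using a one tailed analysis (assuming superior results with the kFA), an alpha value of 0.05 and power of 0.80". The target difference is 12 points on the Forgotten Joint Score (FJS), which 6.1 calls the minimal clinically important change. Drop-out is 10% and the total is 100. Section 3.5 gives "the minimum of 90 patients required to answer the study question", that is 45 per arm. The only variability quoted comes from the initial cohort: "the mean FJS score at 1 year in the mFA TKA was 59 (SD 6) and in the kFA TKA was 75 (SD 8").

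**Primary analysis (6.2.1).** "The analysis of the per-protocol population will be considered the primary analysis". For the comparison itself, "a two-sided confidence interval for the difference between the changes from baseline will be calculated". The next sentence sets the level: "This confidence interval will cover the true difference in the percentage change from baseline with a probability of 95" per cent.

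**Testing convention (6.2.2).** Under the secondary endpoints, but worded for every test: "All tests will be declared statistically significant if the calculated p-value is less or equal to 0.05", and "All tests will appear as two-sided p-values".

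Section 2.1 states the null hypothesis as no difference between the groups. No section plans a one-sided test or a 90% interval.

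**The concern.** A two-sided 95% interval excludes zero in favour of functional alignment (FA) only when the one-sided p-value is below 0.025. The trial was sized for a one-sided threshold of 0.05. The 80% in 6.1 is therefore the power of a more lenient test than the one in 6.2.1.

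Two things are at stake.

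- **Reading a null result.** It would be judged against 80% power. If that figure is right for the one-tailed test, the planned interval misses a true 12-point benefit about 30% of the time, not 20%.
- **Reading a borderline result.** Section 6.2.1 has no decision rule. A one-sided p-value between 0.025 and 0.05 could be called positive by appeal to 6.1 and not positive by appeal to 6.2.1.

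A reader cannot correct the power unaided, because the SD that produced 45 per arm is not given.

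**Working it through.** **Inputs.** Difference 12 points, one-tailed alpha 0.05, power 0.80, drop-out 10%, total 100, SDs 6 and 8 (all 6.1); 45 evaluable per arm (3.5); two-sided 95% interval (6.2.1). The SDs pool to √((36+64)/2) = 7.07.

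**Step 1: try to reproduce N.** Normal approximation: n per arm = 2·SD²·(z_α + z_β)²/12², with z_0.95 + z_0.80 = 1.645 + 0.842 = 2.487 one-tailed and 1.960 + 0.842 = 2.802 two-sided.

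- SD 6, one-tailed: 2 × 36 × 6.18/144 = 3.1, so 4 per arm.
- SD 8, one-tailed: 2 × 64 × 6.18/144 = 5.5, so 6 per arm.

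The noncentral t, which is more accurate at such small n, gives:

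| SD | n per arm, one-tailed | n per arm, two-sided |
|---|---|---|
| 6 | 4 | 6 |
| 7.07 | 6 | 7 |
| 8 | 7 | 9 |

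None is near 45. Only the drop-out step reproduces: 90/0.90 = 100.

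**Step 2: the SD that 45 per arm implies.** SD = 12·√(45/2)/(z_α + z_β).

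- One-tailed: 56.92/2.487 = 22.9 (noncentral t: 22.72).
- Two-sided: 56.92/2.802 = 20.3 (noncentral t: 20.09).

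Neither value appears in the documents.

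**Step 3: power of the planned interval if the 80% is accepted.** This needs no SD. If the expected z is 1.645 + 0.842, power at the two-sided 5% level is Φ(1.645 + 0.842 − 1.960) = Φ(0.527) = 0.701. The noncentral t at 45 per arm and SD 22.72 gives 0.698.

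**Step 4: the range by assumed SD of the analysed outcome** (45 per arm, 12 points, noncentral t):

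| SD (assumed) | One-tailed 0.05 | Two-sided 0.05 | Difference detectable, 80% two-sided |
|---|---|---|---|
| 8 | >0.999 | >0.999 | – |
| 20 | 0.881 | 0.804 | 11.9 |
| 22 | 0.822 | 0.725 | 13.1 |
| 22.72 | 0.800 | 0.698 | 13.6 |
| 23 | 0.791 | 0.687 | 13.7 |
| 25 | 0.731 | 0.615 | 14.9 |

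**Step 5: smaller per-protocol set.** The 10% allowance covers drop-out only. If 40 per arm remain (an assumption), two-sided power is 0.755 at SD 20 and 0.645 at SD 22.72.

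**Step 6: which SD is needed.** The cohort SDs describe the 1-year score. Section 6.2.1 analyses change from baseline, the primary endpoint is at two years, and no SD of change is given. Section 6.2.1 also moves from change to percentage change between consecutive sentences. If percentage change is meant, neither the 12-point target nor the table above describes the analysis.

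**The case against.** The strongest reply is that 70% rests on an SD found nowhere in the protocol. With the printed SDs, 45 per arm gives power above 99.9% under either rule and sidedness has no practical effect. With an SD near 20, the planned interval already has 80%. On this view the larger defect is that N does not follow from its inputs.

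Much of that stands. The 70% is only what follows from accepting the protocol's own 80%; it is not an estimate of the trial's actual power. But the printed SDs do not rescue 6.1, because they cannot produce 90 evaluable patients. Some other SD, or some other reasoning, lies behind the number.

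A second reply is that 6.2.1 describes estimation without a decision rule, and that the two-sided convention sits under secondary endpoints. A one-sided test reported beside a 95% interval is not expressly excluded. That is possible, but it is not planned anywhere. The null of no difference in 2.1 and the wording of 6.2.2 both favour the two-sided reading.

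A third reply is that the error is harmless, since the interval is the stricter rule. It is true that type I error is not inflated. The cost falls on power and on how the result will be read.

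**Conclusion.** The concern holds. The stated 80% is the power of a one-tailed 0.05 test, and the planned primary analysis is a two-sided 95% interval.

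Taking the 80% at face value, power for 12 points under the planned interval is about 70%, and the difference detectable with 80% power is about 13.6 points, above the protocol's own minimal important change. This assumes 45 evaluable per arm, equal variances, and an interval read as a two-sided 5% test.

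The actual power cannot be determined from the documents. It depends on the unstated SD of the two-year change in the per-protocol population: about 80% at SD 20, 70% at 22.7 and 61% at 25. The stated SDs of 6 and 8 are not consistent with N = 100.

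**What to change.** **In 6.1**, replace the one-tailed sentence with text on these lines:

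> The calculation uses a two-sided alpha of 0.05, matching the two-sided 95% confidence interval in 6.2.1. It assumes an SD of [x] for the change in FJS from baseline to two years ([source]). With 90 evaluable patients (45 per group), power to detect a 12-point difference is [y]%.

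Derive [y] from the SD given (Step 4 shows the range), and explain how that SD relates to the cohort values of 6 and 8.

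**In 6.2.1**, add:

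> Superiority of FA will be concluded only if the two-sided 95% confidence interval for the FA minus MA difference lies entirely above zero.

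In the same paragraph, say whether absolute or percentage change is analysed. The 6.1 wording above assumes absolute change.

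A pre-specified one-sided 0.05 rule (equivalently a 90% interval) would also remove the mismatch, but it relaxes the interval already planned. Whichever is chosen should be documented before the two-year data are analysed.

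**Cost.** One paragraph in 6.1 and a sentence or two in 6.2.1. The sponsor has to find and name the planning SD, and the stated power may become less favourable. Correcting the text needs no change in N. Restoring 80% two-sided power at the implied SD of 22.7 would be a separate decision: 58 per arm, 116 evaluable, and 116/0.90 = 129 enrolled. The study summary has recruitment ending in 12/2021 and this version is dated 14/10/2021, so restating the power is the practical route.

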6.2 Endpoint Analysis

6.2.1 Primary Endpoint

The analysis of the per-protocol population will be considered the primary analysis. The differences

between the MA TKA and FA TKA groups will be analysed by calculating the difference from baseline, per patient, and a two-sided confidence interval for the difference between the changes from baseline will be calculated. This confidence interval will cover the true difference in the percentage change from baseline with a probability of 95%.

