1.2 Need for a trial

There is a need for high quality evidence on the clinical and radiological benefits of functionally aligned TKA. This study would show if there is any superior outcomes to be obtained from functional alignment. Clinical and functional outcomes should also be correlated to longer-term outcomes to better establish the “safe zone” for functional alignment.

Currently the vast majority of TKA throughout the world is undertaken utilizing MA alignment. Any change to a newer technique from the current ‘gold standard’ would need to be justified by improved clinical outcomes as there is no long term longevity data for Functional Alignment. Both surgeons and patients are only able to consider the relative risks and benefits of this technique once they are defined by sound scientific evidence. This study will contribute to the body of this evidence.

2. Objectives

The overall aims of this prospective, randomised double-blinded controlled trial are to compare functional, clinical, and radiological outcomes in FA TKA versus MA TKA. Patients undergoing MA TKA will form the control group and those undergoing FA TKA will form the investigation group. A superiority design will be used to evaluate whether FA TKA provides superior outcomes compared to MA TKA. Primary and secondary objectives will be used to quantify and draw inferences on differences in the efficacy of treatment between the two groups. To ensure accuracy of planning and implantation robotic arm assisted surgery will be utilized in both groups (Stryker MAKO, Fort Lauderdale, FL). Standardised post-operative care will be undertaken to ensure the only difference between groups is alignment of implants.

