3.7 Surgical Intervention: MA vs. FA TKA

All patients undergoing TKA will undergo preoperative CT scan of the leg to establish the extent of the disease process, determine bone resection, and plan implant sizing and positioning. The preoperative CT scan will be used to create individualized plans for achieving mechanical and kinematic alignment and stored within the robotic program that is used during the operative procedure. This will ensure that all implants and equipment for achieving either mechanical alignment or functional alignment are ready and available for use in theatre. These

plans will provide the initial point from which functional alignment will be achieved.

Following informed consent and randomisation into one of the two treatment groups, patients will undergo robotic-arm assisted TKA by one of the participating surgeons. Surgery in both groups will be undertaken through the standard anteromedial arthrotomy with positioning of reference pins in the femur and tibia for registration of the hip centre, ankle position and limb alignment. The femur will be prepared first in all operations. Cruciate retaining technique will be used in both groups. Interoperative requirement for a more constrained implant will result in exclusion from the study.

In MA TKA, tibial and femoral osteotomies in the coronal plane will be planned perpendicular to the tibial and femoral mechanical axes respectively to achieve neutral overall alignment. Soft tissue balance will be assessed and minor adjustments to bony alignment made to balance the knees with a maximal adjustment of two degrees valgus and two degrees varus of coronal alignment from neutral. Femoral rotation will be planned to surgical epicondylar axis and adjustments to rotation made to allow equal flexion and extension balance (to within 1mm). If balance can not be achieved within these boundaries then soft tissue release will be undertaken.

In the sagittal plane, 0-3 degrees of posterior tibial slope and 0-5 degrees of femoral component flexion will be used to optimise implant sizing whilst preventing notching. In the axial plane, the tibial component aligned to Akagi's line, which connects the medial border of the patellar tendon attachment to the middle of the posterior cruciate ligament.

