In kFA TKA, femoral and tibial osteotomies will be planned for equal bony resections from the femoral condyles to replicate the patients anatomy. In the coronal plane, the distal femoral resection will be 6.5mm from the subchondral bone of both medial and lateral condyles, with compensation for wear by adjusting the resection by 1-3mm. In the proximal tibia, there will be 7mm of resection from the subchondral bone from both the medial and lateral tibial plateau. In the sagittal plane, resection angle will be determined intraoperatively to closely match the native femoral flexion and tibial slope. In the axial plane, posterior femoral resection will be 6.5mm from the subchondral bone of both medial and lateral posterior condyles. Tibial rotation will be aligned to Akagi's line. Adjustments will be made to bony alignment to balance soft tissues within the boundaries of six degrees varus and three degrees valgus Hip-Knee-Ankle (HKA) alignment. Femoral component alignment will be limited to six degrees of valgus and three degrees of varus in the coronal plane. Tibial alignment will be limited to six degrees of varus and three degrees of valgus in the coronal plane. Combined flexion of the components will be limited to ten degrees of flexion. Only if balance can not be achieved within these boundaries will soft tissue release be undertaken.

In both groups, polyethylene thickness will be selected to maximise range of motion whilst avoiding hyperextension and ligament laxity. Tibial depth will be adjusted to maintain insert thickness between 9 and 14mm. Any TKA requiring a 16 mm or greater polyethylene insert thickness will be excluded from the study.

Patients in both groups will undergo the same inpatient and outpatient postoperative rehabilitation programme. Intra-operative data will be recorded using the surgical data form (Appendix 19.7). The only difference between the two treatment groups is that the control group will undergo MA TKA and the investigation group will undergo FA TKA.

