6.4 Per-protocol population

The per-protocol population is defined as all patients who are randomised to MA TKA or FA TKA and complete the study according to the protocol.

In the event that there are errors in the randomisation assignment, the analysis will be performed using the treatment that the patient actually received, not the assigned treatment. Patients will be considered protocol violators if they do not meet the eligibility criteria as outlined in the protocol. Other reasons to be considered a protocol violator include, but are not limited to, protocol violations, and any actions that compromise the effectiveness of the treatment, such as receiving a secondary treatment. Protocol violators will not be considered as part of the per-protocol population and will be listed separately with the reason for their exclusion from the per-protocol population.

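### In a superiority trial the per-protocol set is primary and loses patients for events after randomisation; the intention-to-treat set already defined should be primary, analysed as assigned

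*Combined protocol and SAP*

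**What the plan says.** Section 2 (Objectives) sets the aim: "A superiority design will be used to evaluate whether FA TKA provides superior outcomes compared to MA TKA". Section 6.2.1 then ranks the analysis sets: "The analysis of the per-protocol population will be considered the primary analysis".

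Section 6.4 limits the per-protocol set to randomised patients who complete the study as the protocol requires. Its list of violators is open: "Other reasons to be considered a protocol violator include, but are not limited to, protocol violations". For errors in assignment, "the analysis will be performed using the treatment that the patient actually received, not the assigned treatment".

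Other sections remove patients after allocation:

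- Section 3.7, repeated in 5.1: "Interoperative requirement for a more constrained implant will result in exclusion from the study".
- Section 3.7, repeated in 5.1: "Any TKA requiring a 16 mm or greater polyethylene insert thickness will be excluded from the study".
- Section 4.2: a patient whose implant is revised is withdrawn.

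Section 6.3 defines an ITT set of all randomised patients, whatever their eligibility, treatment received or later withdrawal. It plans follow-up after study exit and imputation, and analyses assignment errors as assigned. It does not say what part this set plays for the primary endpoint. Section 3.6 has the chief investigator told the allocation so that surgery can be planned.

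**The concern.** Randomisation makes the two arms comparable at allocation. A set whose membership depends on what happens in theatre or in the following two years no longer has that guarantee, and in a superiority trial nothing in the text justifies giving it up. The theatre decisions that settle membership are made with the allocation known to the chief investigator and under different limits. Appendix 19.9 allows a hip-knee-ankle angle of 2° varus to 2° valgus in the control arm and 6° varus to 3° valgus in the investigation arm. Unequal removal is therefore possible.

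A knee revised before two years, and so withdrawn, is absent from the primary comparison altogether. Because the violator list is open, exclusions could also be settled after scores are known. At stake is whether the headline FJS result can be read as an effect of the assigned alignment.

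**Working it through.** **The two sets side by side**

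| Event after randomisation | Per-protocol set, primary (6.4) | ITT set (6.3) |
|---|---|---|
| More constrained implant, or insert of 16 mm or more | Out (3.7, 5.1) | In, by the definition of the set |
| Revision | Out (4.2: withdrawn, so not a completer) | In; follow-up sought despite exit |
| Other violation | Out, list open | In |
| Assignment error | By treatment received | By assigned arm |
| Intraoperative conversion | Not stated | ITT and treatment received named together |

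Only the right-hand column keeps the randomised comparison, and its conversion row needs one clarifying sentence.

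**The plan's own figure.** Sections 3.5 and 6.1 give 90 completers, 45 per arm, and 90 / (1 − 0.10) = 100, which reproduces. The 90 does not follow from the SDs quoted in 6.1 (6 and 8, for the 1-year score): pooled SD = √((36 + 64)/2) = 7.07, and 2 × (1.645 + 0.842)² × 7.07² / 12² = 4.3, or 5 per arm. That is a separate matter. Here it means that the SD of the analysed change is not in the documents, so two values are carried:

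- SD 7.07, from the quoted SDs. Standard error = 7.07 × √(2/45) = 1.49.
- SD 22.7, an assumption, back-solved by noncentral t from 45 per arm, 12 points, one-tailed 5% and 80% power. Standard error = 22.7 × √(2/45) = 4.79.

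**Bias illustration (removal rates and score gaps are assumed).** If a fraction f of an arm is removed, and those patients score g points below the rest of the arm, the retained mean exceeds the full-arm mean by f × g. The contrast shifts by the difference in f × g between arms. With equal g, an excess removal of 5% and a gap of 10 points gives 0.05 × 10 = 0.5 points; 10% (5 of 50) and 30 points gives 0.10 × 30 = 3.0 points, a quarter of the 12-point target. The sign depends on which arm loses more.

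Probability that the two-sided 95% interval excludes zero with no true effect, 45 per arm, noncentral t on 88 degrees of freedom with noncentrality shift / standard error:

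| Shift | SD 22.7 | SD 7.07 |
|---|---|---|
| 0.5 | 0.5/4.79 = 0.10 → 5.1% | 0.5/1.49 = 0.34 → 6.3% |
| 3.0 | 3.0/4.79 = 0.63 → 9.5% | 3.0/1.49 = 2.01 → 51% |

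The last cell is an extreme: a 30-point gap is 30/7.07 = 4.2 SDs.

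**Cost of ITT in power.** Assume SD 22.7, a two-sided 5% test, and a 12-point effect reduced by dilution to 12 × 0.9 = 10.8 or 12 × 0.8 = 9.6 points.

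| Dilution (assumed) | 45 observed per arm | 50 observed per arm |
|---|---|---|
| None | 70% | 74% |
| 10% | 61% | 65% |
| 20% | 51% | 55% |

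The right-hand column is an upper limit, because imputation does not restore lost information.

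**The case against.** The strongest reply is that no harm is shown. The documents give no removal or conversion rates, and equal removals with equal score gaps would cause no bias. Reaching the alignment limits does not itself remove a patient. In the control arm, "If balance can not be achieved within these boundaries then soft tissue release will be undertaken"; in the investigation arm, "Only if balance can not be achieved within these boundaries will soft tissue release be undertaken". Tibial depth is also adjusted in both arms to hold insert thickness. All of this stands. A reader might infer that the plan favours functional alignment because the control limits are narrower; the documents do not support that, or any other direction.

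Three other strong readings also go too far:

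- **That the ITT set must contain people who never consented.** Sections 3.4, 3.6 and 5.0 describe randomisation on agreement with signed consent later, but 3.6 also allocates in order of consent, and 3.7 names consent before randomisation. The order is in conflict, not settled.
- **That section 4.2 bars data after revision.** Using data up to withdrawal can mean only that data already collected are kept. Section 6.3 seeks later follow-up.
- **That complete release of the posterior cruciate ligament (PCL) leads to exclusion.** Section 5.1 retains patients with PCL release; Appendix 19.9 converts complete release to a PS component. This conflicts with 3.7 only if PS counts as more constrained, which no section says.

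It is also fair that ITT would not count a revision as a failure in itself. It would keep the knee, and its FJS where obtained, in the comparison. Dilution is a real cost. None of this supplies a reason for ranking per-protocol first.

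**Conclusion.** The point holds as a defect in the primary analysis and must be fixed. It rests on sections 2, 6.2.1, 6.3 and 6.4 as written and needs no assumption about SD or removal rates. The plan gives up the randomised comparison for its main result although a suitable ITT set stands in the next section.

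It does not establish that the result will be materially biased, or towards which arm. The rejection rates of about 10% and 51% for a 3-point shift show only how strongly the consequence depends on an SD that the documents do not settle; the shift itself is assumed. The unclear rules on PCL release and on the order of consent are matters for clarification and do not carry the conclusion.

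**What to change.** **Changes**

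- **6.2.1:** make the ITT set of 6.3, analysed by assigned arm, primary for 2-year FJS, with per-protocol as a sensitivity analysis.
- **6.3:** state that intraoperative conversions are analysed as assigned in the primary analysis and that any as-treated analysis is supplementary.
- **6.4:** replace the open violator list with a closed one, fixed without reference to outcome.
- **3.7, 4.2 and 5.1, for analysis purposes only:** state that patients excluded in theatre or withdrawn for revision stay in the ITT set and that their 2-year FJS is sought, as 6.3 already intends. Patients who withdraw consent contribute data to that point.

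**Clarifications**

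- Reconcile 5.1 with 3.7 and Appendix 19.9 on complete PCL release with a PS component.
- Reconcile the order of randomisation and written consent across 3.4, 3.6, 3.7 and 5.0, and say how patients who decline before written consent are counted and reported by arm.

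**Cost.** This is mainly a protocol amendment. The ITT set, follow-up intent and interim FJS visits exist, and the form in Appendix 19.8 already records alignment theory, PCL release, insert thickness and implant type. The price is the possible dilution shown in the power table. In addition, this version is dated October 2021 and recruitment was planned from March 2021, so patients already excluded may lack 2-year scores; their number should be reported by arm.

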2.1 Primary objective

- The primary objective of this study is to compare clinical outcomes at two years following surgery between FA TKA and MA TKA. The primary outcome measure for this study is the Forgotten Joint Score (FJS) at two years after surgery. The null hypothesis is that there is no difference in functional scores at two years following surgery between patients undergoing MA TKA (control group) versus FA TKA (investigation group). The hypothesis is that outcome measures obtained at two years after surgery in patients undergoing FA TKA are not achievable using MA TKA. Further PROMs will be used to further assess clinical outcomes including Forgotten Joint Score (FJS), Oxford Knee Score (OKS), Knee injury and osteoarthritis outcome Junior score (KOOS Jr), VAS Pain, and Kujala scores preoperatively and postoperatively at 3 months, 1 year and 2 years. Also health-related quality of life will be measured using European Quality of Life questionnaire with 5 dimensions for adults (EQ-5D-5L) preoperatively and postoperatively at 3 months, 1 year and 2 years. Range of movement (degrees) in knee joint during inpatient admission and postoperatively at 6 weeks, 3 months, 1 year and 2 years.

2.2 Secondary objectives The secondary objectives of the study are:

- Determine lower limb alignment achieved with both alignment techniques. Lower limb alignment as assessed using standing long leg x-rays performed postoperatively at 3 months. Measurements of the hip-knee-angle (HKA), medial proximal tibial angle (MPTA) and lateral distal femoral angle (LDFA). Also evidence of imbalance with implant lift off will be measured.

- Determine if there are any differences in analgesic requirements based on alignment method used. Analgesia requirements during inpatient admission and postoperatively at 6 weeks, 3 months, 1 year and 2 years will be measured.
- Determine whether alignment method utilized has an effect on the sagittal stability of the TKA. Assessment of sagittal stability at Preop, 3 months, 1 year and 2 years will be undertaken with an arthrometer “Lachmeter”.
- Determine whether alignment method utilized has an effect on functional outcomes. This will be assessed by a combination of
 - Maximum voluntary isometric force using a hand-held dynamometer at Preop, 3 months, 1 year and 2 years.
 - Sit to stand values as measure of function at Preop, 3 months, 1 year and 2 years.

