3.10 Clinical and radiological assessment

The FJS, EQ5D-5L, OKS, VAS Pain, Likert scale, KOOS Jr and Kujala Anterior knee pain scores are validated tools for the clinical assessment of patients after knee arthroplasty (10,11,18,19). Each of these scores is completed preoperatively and then at regular intervals during follow-up (Appendix 19.1). This information is routinely discussed at each of these outpatient consultations but patients in this study will have the information recorded within these validated questionnaires to facilitate data analysis.

Routine clinical measures of height, weight, range of movement and pain description will be taken. To test endurance and strength, a 30 sec Sit to stand test will be measured. This test asks the participant to stand up / sit down from a standardised chair height within 30 seconds (Appendix 19.6). To measure the AP stability of the knee (20), a lachmeter reading will also be recorded at the post operative intervals and to measure strength, a hand

held dynamometer test will also be performed.

	Preoperative	Discharge	6 weeks	3 months	1 year	2 years
Patient demographics	X					
Patient medical history	X					
Operation details		X				
Clinical history and PROMS (FJS, EQ5D-5L, OKS, VAS pain, KOOS Jr, Kujala Anterior Knee Pain, Likert scale)	X		X (FJS and VAS only)	X	X	X
Functional Examination (Lachmeter testing, Range of Movement, Hand Held Dynamometer, 30s STS test)	X	X (range only)	X (range only)	X	X	X
Adverse Events	At occurrences through study period					

Table 1. Timelines for clinical data collection in all study patients.

	Preoperative	Discharge	6 weeks	3 months	1 year	2 years
Plain knee joint radiographs	X	X			X	X
Plain long-leg radiographs	X			X		
CT Knee joint	X					

Table 2. Timelines for radiological data collection in all study patients. Assessment windows will be as followed; 6 weeks review (± 1 week), 3 month review (± 2 weeks), 12 month review (± 2 months), 2 year review (± 2 months).

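### The primary outcome is defined and sized as the two-year FJS, but 6.2.1 analyses an unadjusted change from baseline and then puts its interval on a percentage scale; adjusting for baseline would be at least as precise at almost no cost

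*Combined protocol and SAP*

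**What the plan says.** Section 2.1 states: "The primary outcome measure for this study is the Forgotten Joint Score (FJS) at two years after surgery". Section 6.1 repeats it as "Functional outcome as assessed using the FJS score at two years" and adds: "The study was powered to demonstrate a 12 point difference in the Forgotten Joint score". The SDs printed there are SDs of a follow-up score, not of a change, and they belong to one year: "the mean FJS score at 1 year in the mFA TKA was 59 (SD 6"), with 75 (SD 8) for the kFA group.

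Section 6.2.1 (Primary Endpoint) takes another route. The group differences "will be analysed by calculating the difference from baseline, per patient", with a two-sided 95% interval for the difference between the two groups' changes. The next sentence describes the same interval as covering a difference in percentage change. The section names neither the FJS nor the two-year visit.

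No analysis with a baseline covariate appears anywhere in the available text. The methods listed in 6.2.2 are for secondary endpoints and do not include one. The baseline value will exist: section 3.10 says "Each of these scores is completed preoperatively and then at regular intervals during follow-up", its Table 1 includes the FJS preoperatively, and so does the preoperative case report form in Appendix 19.1.

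**The concern.** The outcome is a score at one time point, and so is the quantity used for sizing. The planned analysis is a difference of two scores. Subtracting the preoperative score fixes the slope of two-year score on preoperative score at 1. If the true slope is lower, the subtraction adds noise, and with a weak correlation it can do worse than ignoring baseline altogether. The primary interval may then be wider than the collected data allow, in a trial that expects only about 90 completers.

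The percentage sentence is a separate inconsistency. A percentage change divides by each patient's own preoperative score, so it is not on the scale of the 12-point target. As written, 6.2.1 contains two different primary analyses, and neither is on the two-year score itself.

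**Working it through.** **Inputs from the documents.** Target difference 12 points; one-tailed alpha 0.05; power 0.80; 45 completers per arm (3.5, 6.1); one-year SDs 6 and 8 (6.1); two-sided 95% interval (6.2.1).

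**Inputs not in the documents.** The preoperative SD s0, the two-year SD s1, and their correlation r. These are assumed below and shown over a range. Write k = s0/s1.

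**Step 1: the plan's own sample size.** Pooled SD = √((36 + 64)/2) = 7.07. By the normal approximation, n per arm = 2 × 50 × (1.645 + 0.842)²/144 = 4.3, so 5 per arm, 10 in total, and 12 after 10% dropout. The plan states 90 and 100. The printed SDs therefore do not reproduce N = 100. Solving instead for the SD that gives 80% one-tailed power at 45 per arm (noncentral t, 88 df) gives 22.7; the normal approximation gives 22.9. I use 22.7 as s1.

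**Step 2: the right comparator.** At SD 22.7 the standard error is 22.7 × √(2/45) = 4.79. The plain two-year score has 80% power one-tailed but 70% two-sided. Since 6.2.1 is two-sided, 70% is the reference.

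**Step 3: variances per patient.**
- Change score: s1²(1 + k² − 2rk)
- ANCOVA: s1²(1 − r²)
- Difference: s1²(k − r)² = (s0 − r·s1)², which is never negative.

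This is a large-sample result. Estimating the slope costs ANCOVA about 1% of variance at 90 patients. The change score is less precise than the plain two-year score when r < k/2.

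Example, k = 1 and r = 0.2. The change-score SD is 22.7 × √1.6 = 28.7. The ANCOVA SD is 22.7 × √0.96 = 22.2. The variance ratio is 1.6/0.96 = 1.67.

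**Step 4: two-sided power at 45 per arm, 12 points, s1 = 22.7** (slope-estimation cost ignored).

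| k = s0/s1 | r | Change score | ANCOVA |
|---|---|---|---|
| 1.0 | 0.2 | 50% | 72% |
| 1.0 | 0.3 | 55% | 74% |
| 1.0 | 0.5 | 70% | 82% |
| 1.0 | 0.7 | 89% | 94% |
| 0.6 | 0.3 | 70% | 74% |
| 0.6 | 0.5 | 81% | 82% |
| 0.6 | 0.6 | 87% | 87% |

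**Step 5: the printed SDs.** With s1 = 7.07 and a preoperative SD of the same size, the change-score SD even at r = 0 is 7.07 × √2 = 10.0. Power at 45 per arm is then above 99.9% for both methods.

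**The case against.** The strongest reply is that the planned estimator is valid. Allocation is random, so the preoperative means have the same expectation in both arms, and the difference in mean change equals in expectation the difference in mean two-year score. The interval has correct coverage. On the documents' own SDs nothing practical is lost, and a large loss needs three unprinted conditions together: an SD near 22.7, a low correlation, and similar SDs at the two visits. All of this stands, and it limits how serious the point is. It does not defend the plan's choice, because the alternative needs no new data and costs about 1% of variance at worst.

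Four stronger readings are tempting, and the documents do not support them.

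- **Bias or a different estimand.** A reader might infer that change from baseline answers a different question. On the absolute scale it does not. Only the percentage sentence changes the quantity estimated.
- **Chance baseline imbalance as a further harm.** It is already contained in the variance of the change score, so listing it separately would count it twice.
- **A drop from 80% to 50%.** Ten points of that gap come from sizing one-tailed and analysing two-sided, which is a separate matter. The fair comparison at r = 0.2 with equal SDs is 50% against 70% for the plain score and 72% for ANCOVA.
- **ANCOVA always strictly better.** When r is close to s0/s1 the two methods are equal, and the change score can be trivially ahead once the slope has to be estimated.

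**Conclusion.** The point holds as a recommendation that should be adopted. It does not invalidate the planned comparison. Two things are certain from the text: the analysis in 6.2.1 does not match the outcome defined in 2.1 and sized in 6.1, and 6.2.1 contradicts itself on absolute against percentage change. The loss of precision is conditional. If the two-year SD is near 22.7, it ranges from 22 percentage points of two-sided power (equal SDs, r = 0.2) to none (preoperative SD 60% of the two-year SD, r = 0.6). It is negligible at the printed SDs of 6 and 8 if the preoperative SD is similar, although those SDs cannot be squared with a target of 100 patients. The preoperative SD and the correlation are assumptions throughout.

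**What to change.** In 6.2.1:

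- Name the outcome and visit, and make the primary analysis a linear model of two-year FJS with treatment arm and preoperative FJS as terms.
- Report the adjusted mean difference in FJS points with its two-sided 95% confidence interval.
- Delete the reference to percentage change.
- Keep change from baseline as a descriptive summary only.

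In 6.1, leave the SDs labelled as one-year values. Relabelling them as two-year SDs would be false, since the plan states no two-year SD.

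The cost is a few sentences of plan text and one degree of freedom. No extra data are needed. The change should be made before outcomes are seen by arm, so that the choice of adjustment cannot look data-driven.
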